4.5.3.2. Vital Signs

A summary of change from baseline vital sign values will be provided by visit and intervention group, including systolic blood pressure, diastolic blood pressure, heart rate, respiratory rate, height, weight and BMI, with a summary of baseline values included in the table.

The number and percentage of participants with clinical important changes for vital signs (systolic blood pressure, diastolic blood pressure, heart rate) will be generated using the PCI criteria stated in Section 6.2.1.3.

The mean of replicate assessments will be used as baseline and as value at each timepoint for blood pressure and heart rate values collected in triplicates.

4.5.3.3. ECG

The QTc data analysis will use the collected values based on Fridericia formula. The number and percentage of participants with clinical important changes for 12-lead ECG will be generated using the PCI criteria stated in Section 6.2.1.2.

For all ECG analyses, baseline is taken to be the mean of the triplicate values collected pre-1st skin challenge.

The following summaries will be provided by visit:

- Summary of ECG findings (the clinical significance and interpretation of each planned ECG). In the case of triplicate ECG measurements, results will be presented separately by measurement number.
- Summary of change from baseline in ECG values. In the case of triplicate ECG measurements, summaries will use the average of the triplicate, listings will present all individual measurements (and the average).

The absolute and change from baseline ECG values will be rounded to the nearest integer before being categorized according to the clinical concern ranges. The following summaries of participants will be produced:

- A summary of QTcF absolute values will display the number and percentage of participants with a post-baseline increase to a value within each clinical concern range for the worst-case post-baseline only.
- A summary of change from baseline QTcF values will display the number and percentage of participants with a change within each range for the worst-case post-baseline. Participants with missing baseline values will be excluded from this summary.

4.6. Other Analyses

Not applicable.

4.6.1. Subgroup analyses

Not applicable

4.6.2. Other variables and/or parameters

Not applicable

4.7. Data reviews

All data reviews will be performed by the data review committee (DRC) (see Section 10.1.5 of the protocol) in accordance to the Dose Escalation Plan and are summarised in

Table 1. Study population and safety data will be generated by the site, wheal and flare data will be generated by S&P.

Table 1 Timing, purpose, outcomes and data to be reviewed at each data review

Data review number	Timing	Purpose	Potential outcomes	Data to be reviewed
1.1	~3 participants who have completed the part 1 challenge visit	Review safety data Review PD data	Stop/pause study or recommend alterations to study design or conduct for safety Modify SP concentrations for the next participants to be enrolled in part 1 Continue recruitment to part 1 at the same SP concentrations	Study population Safety Wheal response (plots)
1.2	~6 participants who have completed the part 1 challenge visit	Review safety data Review PD data	Stop/pause study or recommend alterations to study design or conduct for safety Modify SP concentrations for the next participants to be enrolled in part 1 Stop recruitment to part 1 and open up part 2 Continue recruitment to	Study population Safety Wheal response (plots)

Data review number	Timing	Purpose	Potential outcomes	Data to be reviewed
			part 1 at the same SP concentrations	
1.3	~12 participants who have completed the part 1 challenge visit	Review safety data Review PD data	Stop/pause study or recommend alterations to study design or conduct for safety Confirm SP concentrations for part 2 Stop the study	Study population Safety Wheal response (plots, summary tables) Flare response (plots, summary tables)
2	~10 participants who have completed the part 2 challenge visit 2	Review safety data Review PD data	Stop/pause study or recommend alterations to study design or conduct for safety Continue recruitment to part 2 Stop the study	Study population Safety Wheal response (plots, summary tables, stats analyses) Histamine concentrations (plots, summary tables) if available

4.8. Changes to Protocol Defined Analyses

There were no changes or deviations to the originally planned statistical analysis specified in the protocol 2019N419175_00 (Dated: 03-NOV-2020).

5. SAMPLE SIZE DETERMINATION

A sufficient number of participants will be screened in order to enroll approximatively 32 participants in the study (up to 12 in part 1 and up to 20 in part 2). The sample size for part 1 and part 2 is not based on statistical considerations and is based on previous published data.

6. SUPPORTING DOCUMENTATION

6.1. Appendix 1 Study Population Analyses

The study population analyses will be based on the Screened (Section 6.1.1) and Enrolled (Section 6.1.1, Section 6.1.2, Section 6.1.3, Section 6.1.4) populations.

Study population analyses including analyses of participant's disposition, protocol deviations, demographic and baseline characteristics, prior and concomitant medications, and study intervention will be provided.

6.1.1. Participant Disposition

A summary of the number and percentage of participants who completed the study as well as those who prematurely withdrew from the study will be provided. Primary reasons for study withdrawal will be summarized.

A summary of study intervention status will be provided. This display will show the number and percentage of participants who have completed the scheduled study intervention, or have discontinued study intervention prematurely, as well as primary reasons for discontinuation of study intervention.

6.1.2. Demographic and Baseline Characteristics

The demographic characteristics including age, race, ethnicity, sex, height, screening body weight and Body Mass Index (BMI) will be summarized with descriptive statistics.

In addition, the following age categories will be summarized: 18-64, 65-84 and ≥ 85 .

Summary of race and racial combinations will also be summarised.

Medical conditions collected at screening will be summarized by past and current.

6.1.3. Protocol Deviations

Important protocol deviations (including deviations related to study inclusion/exclusion criteria, conduct of the trial, participant management or participant assessment) will be summarized.

Protocol deviations will be tracked by the study team throughout the conduct of the study. These protocol deviations will be reviewed to identify those considered as important as follows:

- Data will be reviewed prior to freezing the database to ensure all important deviations are captured and categorised on the protocol deviations dataset.
- This dataset will be the basis for the summaries of protocol deviations.

6.1.4. Prior and Concomitant Medications

Concomitant medications will be coded and summarized using the GSK Drug dictionary.

A summary of the number and percentage of subjects with concomitant medications will be displayed using the Generic Term without regard to ATC classifications. This summary will present single ingredient medications and multi-ingredient medications according to the combination of the ingredients. Multi-ingredient medications will be labelled according to the sum of their ingredients, i.e., Generic Term, e.g., “Tylenol Cold and Flu” would appear as “CHLORPHENAMINE MALEATE + DEXTROMETHORPHAN HYDROBROMIDE + PARACETAMOL + PSEUDOEPHEDRINE HYDROCHLORIDE”.

Concomitant medications include any medication that was taken at some point during the on-intervention period as defined in Section [6.2.2.1](#).

6.1.5. Study Intervention Compliance

Not Applicable.

6.1.6. Additional Analyses Due to the COVID-19 Pandemic

Not Applicable.

6.2. Appendix 2 Data Derivations Rule

6.2.1. Criteria for Potential Clinical Importance

The following criteria will be used to flag potential clinical importance:

6.2.1.1. Laboratory Values

Haematology				
Laboratory Parameter	Units	Category	Clinical Concern Range	
			Low Flag (< x)	High Flag (>x)
Haematocrit	Ratio of 1	Male		0.54
		Female		0.54
		Δ from BL	↓ 0.075	
Haemoglobin	g/L	Male		180
		Female		180
		Δ from BL	↓ 25	
Platelet Count	x10 ⁹ / L		100	550
White Blood Cell (WBC)				
Absolute Count	x10 ⁹ / L		3	20
Neutrophil Count	x10 ⁹ / L		1.5	
Lymphocytes	x10 ⁹ / L		0.8	

Clinical Chemistry				
Laboratory Parameter	Units	Category	Clinical Concern Range	
			Low Flag (< x)	High Flag (>x)
Albumin	mmol/L		30	
Calcium	mmol/L		2	2.75
Creatinine	mmol/L	Δ from BL		↑ 44.2
Glucose (Fasting)	mmol/L		3	9
Potassium	mmol/L		3	5.5
Sodium	mmol/L		130	150
Total CO ₂	mmol/L		18	32

Liver Function				
Test Analyte	Units	Category	Clinical Concern Range	
ALT/SGPT	U/L	High	≥ 2x ULN	
AST/SGOT	U/L	High	≥ 2x ULN	
AlkPhos	U/L	High	≥ 2x ULN	
T Bilirubin	μmol/L	High	≥ 1.5xULN	
T. Bilirubin + ALT	μmol/L U/L	High	1.5xULN T. Bilirubin + ≥ 2x ULN ALT	

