**Table 1 Protocol-Required Safety Laboratory Assessments**

Laboratory Assessments	Parameters				
Hematology	Platelet Count	RBC Indices: MCV MCH %Reticulocytes		WBC count with Differential: Neutrophils Lymphocytes Monocytes Eosinophils Basophils	
	RBC Count				
	Hemoglobin				
	Hematocrit				
Clinical Chemistry 	BUN	Potassium	Aspartate Aminotransferase (AST)/ Serum Glutamic-Oxaloacetic Transaminase (SGOT)	Total and direct bilirubin	
	Creatinine	Sodium	Alanine Aminotransferase (ALT)/ Serum Glutamic-Pyruvic Transaminase (SGPT)	Total Protein	
	Glucose [non-fasting]	Calcium	Alkaline phosphatase		
Routine Urinalysis	
 
• Specific gravity
 
• pH, glucose, protein, blood, ketones, by dipstick
 
• Microscopic examination (if blood or protein is abnormal)
 
				
Other Screening Tests	
 
• Follicle-stimulating hormone and estradiol (as needed in women of non-childbearing potential only)
 
• Breath alcohol test (as per standard local practice)
 
• Drug screen to include at a minimum: amphetamines, barbiturates, cocaine, opiates, cannabinoids and benzodiazepines)
 
• Smoking test – breath test or urine cotinine, according to local procedures.
 
• Highly sensitive serum or urine human chorionic gonadotropin (hCG) pregnancy test (as needed for women of childbearing potential)
 
• Serology (HIV antibody, hepatitis B surface antigen [HBsAg], and hepatitis C virus antibody)
 
				

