1.1. Objectives and Endpoints

[figure not shown]
Part 1

Objectives	Endpoints
Primary	

 To characterise the wheal response over time following skin challenge with ascending concentrations of SP on a single day 	
 Wheal response during the 2 h post-challenge period area under the curve (AUC) at each concentration of SP
Secondary	

 To characterise the wheal response over time following skin challenge with ascending concentrations of SP on a single day 	
 Wheal response during the 2 h post-challenge period at each concentration of SP (including maximum observed wheal response, time to maximum observed wheal response, time of complete wheal response disappearance)

 To characterise the flare response over time following skin challenge with ascending concentrations of SP on a single day 	
 Flare response during the 2 h post-challenge period at each concentration of SP (including AUC, maximum observed flare response, time to maximum observed flare response, time of complete flare response disappearance)

 To evaluate the safety and tolerability of SP 	
 Incidence of Adverse Events (AE) and Serious Adverse Events (SAE) Incidence of findings of clinical important changes in: 
 vital signs laboratory safety data 12-lead electrocardiogram (ECG)

Part 2

Objectives	Endpoints
Primary	

 To compare the wheal response over time following skin challenge with ascending concentrations of SP on two days 	
 Wheal response during the 2 h post-challenge period (AUC) at each concentration of SP across 2 challenge days
Secondary	

 To characterise the wheal response over time following skin challenge with ascending concentrations of SP on two days 	
 Wheal response during the 2 h post-challenge period at each concentration of SP across 2 challenge days (including maximum observed wheal response, time to maximum observed wheal response, time of complete wheal response disappearance)

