4.5.3. Additional Safety Assessments

4.5.3.1. Laboratory Data

Summary tables for haematology and chemistry laboratory tests as well as urine concentration parameters will be produced:

- Change from baseline in laboratory parameters (clinical chemistry and hematology) will be presented for continuous variables, with a summary of baseline values included in the tables.
- Summaries of worst-case results post-baseline relative to baseline will be provided for the following tests:
 - For lab tests with associated Potential Clinical Importance (PCI) criteria: the summary will include baseline data and worst-case post-baseline. The baseline categories are: Low, W/in Range and High. The change categories are: To Low, To w/in Range or No Change, To High. If a subject has a decrease to low and an increase to high during the same time interval, then the subject is counted in both the “to Low” and the “to High” categories.
 - For categorical urinalysis parameters

For part 2, change from baseline will be calculated for each visit, (using the visit 1 baseline for visit 1, and visit 2 baseline for visit 2).

Baseline and post-baseline data will be included in these tables. If a participant moves to both a low and a high clinical concern range during the study intervention period, then the participant is counted in both categories.

Summaries of hepatobiliary laboratory events including possible Hy's law cases will be provided in addition to what has been described above. Possible Hy's law cases are defined as any elevated alanine aminotransferase (ALT) $>3\times$ upper limit of normal (ULN), total bilirubin $\geq 2\times$ ULN and alkaline phosphatase (ALP) $<3\times$ ULN/missing. Total bilirubin $\geq 2\times$ ULN can be within 28 days following the ALT elevation and if direct bilirubin is available on the same day, it must be $\geq 35\%$ of total bilirubin.

ALP $<3\times$ ULN/missing means it is satisfied unless the ALP is $\geq 3\times$ ULN at the time of bilirubin elevation. The summary will be produced for worst case post baseline only.

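### The SAP's only creatinine flag is a rise of more than 44.2 mmol/L, which cannot occur; the unit needs correcting, and the glucose, albumin and Total CO2 rows need aligning with protocol Table 1

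*SAP*

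**What the plan says.** The secondary safety endpoints in SAP 1.1 and Protocol Section 3, for both parts, are worded "Incidence of findings of clinical important changes in" vital signs, laboratory safety data and ECG. SAP 6.2.1 supplies the operational rule: "The following criteria will be used to flag potential clinical importance". SAP 4.5.3.1 then builds a worst-case summary on it: "For lab tests with associated Potential Clinical Importance (PCI) criteria: the summary will include baseline data and worst-case post-baseline".

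In the clinical chemistry block of SAP 6.2.1.1:

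- Creatinine has one criterion, a change from baseline: "Creatinine mmol/L Δ from BL ↑ 44.2". The figure is in the high-flag column, so the flag needs a rise above 44.2. There is no absolute limit.
- The glucose row is headed "Glucose (Fasting) mmol/L", with limits of 3 and 9. Protocol Table 1 (Section 10.2) specifies "Glucose [non-fasting".
- Albumin has a low flag at 30 mmol/L, and Total CO2 has limits of 18 and 32 mmol/L. Neither analyte is listed in protocol Table 1.

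SAP 4.5.3.1 also plans a table that does not depend on the flags: "Change from baseline in laboratory parameters (clinical chemistry and hematology) will be presented for continuous variables". SAP 4.8 states that nothing differs from the analyses in the protocol.

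**The concern.** A threshold that cannot be crossed turns a safety count into a fixed zero. Since creatinine has no other criterion in the table, a zero in that row would say nothing about renal safety, and a reader of the report could take it as reassurance.

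The glucose row has a different fault. Limits labelled for fasting samples would be applied to samples taken without fasting, so a high flag could reflect a meal and not the challenge. The albumin and Total CO2 rows ask for output on tests that the protocol does not require.

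**Working it through.** **Inputs.** From the documents: the creatinine trigger of 44.2 mmol/L (SAP 6.2.1.1), the analyte list and glucose condition (protocol Table 1), the sampling times (protocol 1.3.2), and the sample size of up to 12 plus up to 20 (SAP 5). Assumed, because the documents do not give them: creatinine molar mass 113.12 g/mol; albumin molar mass 65 to 69 kg/mol; healthy baseline creatinine 60 to 110 µmol/L, with 40 to 150 as a wider check. The SAP gives no derivation of 44.2, so there is no calculation of its own to reproduce.

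**1. Unit conversion.** mg/dL = mmol/L × molar mass ÷ 10.

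- As printed: 44.2 × 113.12 ÷ 10 = 500 mg/dL (5.0 g/L).
- Read as µmol/L: 0.0442 × 113.12 ÷ 10 = 0.50 mg/dL.
- In reverse: 0.5 mg/dL × 10 ÷ 113.12 × 1000 = 44.20 µmol/L.

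The printed trigger is 1,000 times the µmol/L reading, and the µmol/L reading equals 0.5 mg/dL to three figures.

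**2. Fold-rise needed to flag.** Fold = (baseline + rise) ÷ baseline.

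| Baseline (µmol/L) | Rise of 44.2 mmol/L | Rise of 44.2 µmol/L |
|---|---|---|
| 40 | 1,106 | 2.11 |
| 60 | 738 | 1.74 |
| 110 | 403 | 1.40 |
| 150 | 296 | 1.29 |

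**3. Upper bound on a same-day rise.** Suppose excretion stopped completely. Rise = daily production ÷ 24 × hours ÷ distribution volume. I assume production of 8 to 20 mmol/day and a volume of 25 to 50 L. A Part 1 visit at minimum spacing gives about 1 h (baseline sample to first control) + 0.33 h + 1 h (four injections) + 2 h = 4.33 h; I take 8 h as the long end.

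- Lowest: 8 ÷ 24 × 4.33 ÷ 50 = 0.029 mmol/L (28.9 µmol/L).
- Highest: 20 ÷ 24 × 8 ÷ 25 = 0.267 mmol/L (266.7 µmol/L).

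Even the highest value is about 1/166 of 44.2 mmol/L. Applied in the printed unit, the count is therefore 0 of up to 12 and 0 of up to 20.

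**4. Is the unit an artefact of the PDF text?** Unlikely. The bilirubin rows of the same SAP section keep µmol/L. All seven clinical chemistry rows carry mmol/L, including albumin, where 30 mmol/L would be 30 × 65 to 69 = 1,950 to 2,070 g/L. That pattern fits one unit having been carried down the column.

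**5. SAP 6.2.1.1 against protocol Table 1.**

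- Haematology (haematocrit, haemoglobin, platelets, white cells, neutrophils, lymphocytes): all collected.
- Liver (ALT, AST, alkaline phosphatase, total bilirubin): all collected.
- Calcium, potassium, sodium: collected and consistent.
- Creatinine: collected; the unit is its only fault.
- Glucose: collected, but under the other sampling condition.
- Albumin, Total CO2: not listed.

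So of 6 + 7 + 4 = 17 analytes, two are not protocol-required, one has a label conflict, and one collected analyte has an impossible unit.

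**The case against.** The strongest reply is that little depends on this flag. SAP 4.5.3.1 tabulates continuous change from baseline for all chemistry. Protocol 8.2.4 has the investigator review each laboratory report and record clinically relevant changes as adverse events, and Protocol 10.3.1 counts clinically significant laboratory results as adverse events. The stopping rules in Protocol 7.1 rest on investigator judgement and not on this table. The safety analyses are descriptive, in at most 32 healthy participants. All of this stands. A reader might infer that a creatinine rise would go unseen in the report; the documents do not support that.

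The fixed zero is also conditional. If 44.2 is applied to results held in µmol/L, the flag works. Neither document states the reporting unit of creatinine, and the programming specification that the SAP cites is not available here. This limits the claim but does not remove it, because the SAP as written gives the wrong unit.

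A reader might also conclude that four of the seven chemistry rows cannot work, or that the table as a whole does not fit the samples. That goes too far. Creatinine is in protocol Table 1. Glucose limits of 3 and 9 can be applied to non-fasting values and will fire; the difficulty is interpretation, with too many high flags more likely than too few. Albumin and Total CO2 would produce no output, which is not a false negative, and Protocol 10.2 allows additional tests, so the rows are not necessarily idle.

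**Conclusion.** The point holds as a limited SAP error that should be corrected before the tables are programmed. The printed creatinine criterion is 1,000 times the only plausible reading and cannot be met; in the printed unit the creatinine flag count is zero in both parts. This rests on the molar mass, on any reasonable healthy baseline, and on the SAP being programmed as written. That µmol/L was intended is a strong inference from the match with 0.5 mg/dL, but the sponsor must confirm it.

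The practical effect is small. By the bound above, even a 44.2 µmol/L rise within hours would need excretion to fall severely, so few or no flags are likely with the correct unit. What is lost is the meaning of one descriptive count. The documents do not support reading the whole laboratory endpoint as empty: the haematology and liver rows, and calcium, potassium and sodium, are consistent with protocol Table 1. The glucose label conflict and the two rows without protocol-required data are confirmed and secondary.

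**What to change.** In SAP 6.2.1.1:

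1. **Creatinine.** Confirm the intended unit and correct it to µmol/L (rise above 44.2 µmol/L). Check that the programming specification applies the number to results in that unit.
2. **Glucose.** Reconcile the fasting label with the non-fasting collection in protocol Table 1. If sampling stays non-fasting, either relabel the row and state the basis for the limits, or drop the flag and list glucose against the local laboratory range. The documents contain no non-fasting limits, so the sponsor would have to supply them.
3. **Albumin and Total CO2.** Remove both rows. If they are kept for unscheduled tests, say so and correct the albumin unit.

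The cost is SAP wording and a check of the programming specification. No new data, visits or protocol amendment are needed.

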6.2.1.2. ECG

ECG Parameter	Units	Clinical Concern Range	
		Lower	Upper
Absolute			
Absolute QTc Interval	Msec		> 450
Absolute PR Interval	Msec	< 110	> 220
Absolute QRS Interval	Msec	< 75	> 110
Change from Baseline			
Increase from Baseline QTc	Msec		> 60

6.2.1.3. Vital Signs

Vital Sign Parameter (Absolute)	Units	Clinical Concern Range	
		Lower	Upper
Systolic Blood Pressure	mmHg	< 85	> 160
Diastolic Blood Pressure	mmHg	< 45	> 100
Heart Rate	bpm	< 40	> 110

Vital Sign Parameter (Change from Baseline)	Units	Clinical Concern Range	
		Decrease	Increase
Systolic Blood Pressure	mmHg	≥ 20	≥ 20
Diastolic Blood Pressure	mmHg	≥ 10	≥ 10
Heart Rate	bpm	≥ 15	≥ 15

6.2.2. Study Phase

6.2.2.1. Study phases for concomitant medication

Study Phase	Definition
Prior	If medication end date is not missing and is before 28 days prior to the most recent screening visit assessment
Concomitant	Any medication that is not a prior

Notes:

Please refer to Appendix Section 6.2.7.1: Handling of partial dates for concomitant medication. Use the rules in this table if concomitant medication date is completely missing.

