### 1.3.1. Screening

Visit (V)	V0	Notes
Procedure	Screening (up to 28 days before Day 1)	
Informed consent	X	
Inclusion and exclusion criteria	X	
Demography	X	
Complete physical examination including height and weight	X	
Medical /medication/drug/alcohol/tobacco history	X	Includes Substance usage and current medical condition
Drug/alcohol/cotinine test	X	As per standard local practice
HIV, Hepatitis B and C screening	X	If test otherwise performed within 3 months before first challenge day, testing at screening is not required.
Serum pregnancy test (WCBP only)	X	
FSH and estradiol (in WNCBP)	X	As required, if postmenopausal state in women is in doubt.
12-lead ECG	X	In triplicate. Mean of 3 measure used to confirm eligibility.
Vital signs	X	Blood pressure and heart rate, in triplicate. Mean of 3 measure used to confirm eligibility. Single measurement of temperature.
Control challenge (histamine/saline)	X	
Clinical chemistry/Haematology and urinalysis	X	
SAE review	X	From signing consent

Abbreviations: ECG = electrocardiogram; HIV = human immunodeficiency virus; SAE = serious adverse event; WCBP = women of childbearing potential; WNCBP = women of non childbearing potential.

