### **Prior/Concomitant Therapy**

9. Use of any form of H1 or H2 antihistamine, tricyclic antidepressants, beta2 agonists, dopamine, or beta blocking agents within 14 days before the first challenge visit through final assessments.
10. Use of topical medications such as but not limited to retinoids, steroids, and transdermal hormone replacement therapies on or near the intended site of application within 8 weeks prior to dosing through treatment follow up. Use of other topical preparations such as those containing vitamins, supplements or herbal within 2 weeks prior to dosing through treatment follow up.
11. Past or intended use of any other non-topical over-the-counter or prescription medication, including herbal medications, within 7 days before the first challenge visit, unless, in the opinion of the investigator and GSK Medical Monitor, the medication will not constitute a risk when taking the study intervention or interfere with the interpretation of data.

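### The SAP's rule for concomitant medication has no on-intervention period, so drugs stopped before the first challenge in line with the protocol are counted as concomitant

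*SAP*

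**What the plan says.** SAP 6.1.4 states what the summary is meant to contain: "Concomitant medications include any medication that was taken at some point during the on-intervention period as defined in Section" 6.2.2.1. The display itself is a count by drug name: "A summary of the number and percentage of subjects with concomitant medications will be displayed using the Generic Term without regard to ATC classifications". It carries no timing relative to a challenge.

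SAP 6.2.2.1 has two rows. A medication is prior "If medication end date is not missing and is before 28 days prior to the most recent screening visit assessment". It is concomitant if it is "Any medication that is not a prior". Neither row mentions an intervention period, the first challenge or the start date of the medication.

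Three protocol entries set the relevant times:

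- Section 1.3.1: "Screening (up to 28 days before Day 1".
- Exclusion 9 (antihistamines, tricyclics and certain other drugs): "within 14 days before the first challenge visit through final assessments".
- Exclusion 11 (other non-topical medication): "within 7 days before the first challenge visit, unless, in the opinion of the investigator and GSK Medical Monitor" judge the drug acceptable.

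**The concern.** The two SAP sections cannot both be followed. A programmer who applies 6.2.2.1 produces a table that does not match its description in 6.1.4. A reader who trusts 6.1.4 will take every row as use during the challenge period.

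The mismatch matters more here than in most studies. The endpoints are wheal and flare, and exclusion 9 restricts antihistamines and related drugs around the challenges. Counts by generic name put a participant who stopped such a drug in good time in the same row as one who had it on board. The table then suggests use of restricted drugs during the study where there may have been none, and it cannot show whether the restriction was kept.

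The rule also departs from the rest of the SAP. Section 4.5.2 defines emergent adverse events from the first study intervention, and 6.2.3 counts study days from the first skin challenge at Visit 1. Only the medication phases are anchored to screening.

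**Working it through.** The plan states no figure to reproduce, so this is date arithmetic on its definitions.

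**Inputs**

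- S = days from screening to the first challenge, 0 to 28 (Protocol 1.3.1).
- E = days before the first challenge on which a medication ended.
- Look-back of 28 days before screening (SAP 6.2.2.1).
- Windows before the first challenge: 14 days (exclusion 9) and 7 days (exclusion 11).

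**Rule.** A medication is prior if E > S + 28 and concomitant if E ≤ S + 28. The cut-off therefore runs from 0 + 28 = 28 to 28 + 28 = 56 days before the first challenge.

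**Compliant stops labelled concomitant.** A compliant stop has E ≥ 15 under exclusion 9 and E ≥ 8 under exclusion 11.

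- If pre-screening history is in the dataset, the stop days are (S + 28) − 14 = S + 14 for exclusion 9 and (S + 28) − 7 = S + 21 for exclusion 11.
- If only stops on or after the screening day are in the dataset, they are S − 14 and S − 7, or zero where that is negative.

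| S | Cut-off (days before challenge) | Excl. 9, with history | Excl. 9, from screening on | Excl. 11, with history | Excl. 11, from screening on |
|---|---|---|---|---|---|
| 1 | 29 | 15 | 0 | 22 | 0 |
| 7 | 35 | 21 | 0 | 28 | 0 |
| 14 | 42 | 28 | 0 | 35 | 7 |
| 21 | 49 | 35 | 7 | 42 | 14 |
| 28 | 56 | 42 | 14 | 49 | 21 |

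**Which column applies.** Protocol 6.8 requires recording of medication in use at enrolment or received during the study. Medication history is a separate screening item in Protocol 1.3.1, and nothing shows whether it feeds the dataset that 6.2.2.1 classifies. The from-screening columns are therefore secure and the with-history columns are conditional. For exclusion 9 the secure count is at most 28 − 14 = 14 stop days (days -28 to -15), and it is zero when screening is 14 days or fewer before the challenge.

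**Effect of re-anchoring to the first challenge.** No stop before the first challenge is then concomitant, so the counts above fall to zero. However, E = 1 to 14, which are the 14 stop days inside the exclusion 9 window, also become prior. SAP 6.1 mentions prior medications, but 6.1.4 specifies a summary of concomitant medication only. Without a further step, those breaches would leave the summary.

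**The case against.** The strongest reply is that this is a wording mismatch in one descriptive table and that the study controls drug interference elsewhere. Much of that stands:

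- **Control challenges.** Under Protocol 4.1 a participant whose histamine or saline response is unacceptable does not receive Substance P, at either Part 2 visit. A marginal failure at Visit 2 may be retested. This tests directly for suppressed reactivity, although the thresholds are in the SRM and partial suppression might pass.
- **Medication review.** The schedule in Protocol 1.3.2 includes one at challenge visits.
- **Deviations.** SAP 6.1.3 summarises important deviations, including those from eligibility criteria, after review before the database freeze.
- **Listings.** SAP 6.2.7.1 foresees medication listings that show recorded dates, so a true stop date would be visible.
- **Inference.** The AUC models in SAP 4.2.2 and the analysis sets in SAP 3 do not use the prior/concomitant split, and no hypothesis is tested.

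A reader might infer that the table would conceal a drug on board at one Part 2 visit and so leave the comparison of days confounded. The documents do not support that, because the four safeguards above operate independently of this table.

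A wide look-back also has some rationale. Exclusion 10 restricts certain topical products for 8 weeks, or 56 days, before dosing. But the SAP cut-off equals 56 days only when S = 28, it applies to all drugs, and 6.1.4 does not describe the table as a look-back. The contradiction between the two sections remains.

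**Conclusion.** The inconsistency is real. SAP 6.2.2.1 does not define the period that 6.1.4 says it defines, and following it counts as concomitant some medication that ended before the first challenge in compliance with exclusions 9 or 11.

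For exclusion 9 the secure extent is up to about 14 stop days at the longest screening interval. A reader might take 56 days before the challenge, or 42 compliant stop days, as the general size. Those are maxima: they need screening at day -28 and also pre-screening history in the same dataset, which the documents leave open.

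The consequence is a misleading descriptive table. It is not a threat to the wheal or flare estimates. The point merits correction because the table bears on drugs that can alter the primary endpoint and the correction is cheap.

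**What to change.** 1. In SAP 6.2.2.1, anchor the phases to the first skin challenge at Visit 1. Prior: ended before it. Concomitant: ongoing, end date missing, or ended on or after it. Align the sentence in 6.1.4 with this definition.
2. In both Part 1 and Part 2, add a flag or separate row for medication whose use falls inside the windows of exclusions 9 to 11 as the protocol already states them. In Part 2, show it by visit. Re-anchoring alone would move use in the last 14 days before the first challenge into the prior category and out of the only specified summary.
3. State whether medication history from screening enters the dataset being classified.

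The cost is a few lines of SAP text, the revised phase rule and one extra derivation. Steps 1 and 2 use start and end dates already recorded under Protocol 6.8, and no new assessments are needed. How far the flag reaches before screening depends on the answer to step 3.
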